5.3.2 Study Variables

The primary objective of this study is to evaluate the impact of venetoclax monotherapy on the quality of life of subjects with relapsed or refractory chronic lymphocytic leukemia (CLL). Quality of life will be assessed by the GHS/QoL subscale of the EORTC QLQ-C30.

The secondary objectives are to evaluate the impact of venetoclax monotherapy on quality of life based on the EORTC QLQ-CLL16, EQ-5D-5L, and the remaining subscales/items from the EORTC QLQ-C30; overall response rate (ORR); complete remission rate (CR + CRi); duration of overall response (DOR), time to progression (TTP), duration of progression-free survival (PFS); overall survival (OS); and CR rate in BCRi treated subjects.

Analyses of these endpoints are described in Section [8.0](#).

5.3.2.1 Primary Variable

The primary endpoint will be based on the mean change from baseline to Week 48 on the GHS/QoL subscale of the EORTC QLQ-C30. Subjects will complete the EORTC QLQ-C30, along with other PRO measures, at baseline (within 72 hours prior to the first dose of venetoclax), Week 4, Week 8, Week 12, Week 24, Week 36, and Week 48, then every 12 weeks thereafter until the end of treatment (Week 108). The GHS/QoL subscale will be calculated as per the EORTC scoring manual, and summarized (mean, std dev, median) at each visit.

5.3.2.2 Secondary Variables

Secondary variables include assessments of quality of life based on the EORTC QLQ-CLL16, EQ-5D-5L, and the remaining subscales/items from the EORTC QLQ-C30; overall response rate (ORR); complete remission rate (CR + CRi); duration of overall

response (DOR), time to progression (TTP), duration of progression-free survival (PFS); overall survival (OS); and the CR rate in BCRi treated subjects.

5.3.2.2.1 Quality of Life Assessments

EORTC QLQ-C30

Quality of life and symptoms will be assessed with the European Organization for Research and Treatment of Cancer (EORTC) Quality of Life Questionnaire Core 30 (EORTC-QLQ-C30) version 3.³⁶ The QLQ-C30 is a 30-item subject self-report questionnaire composed of both multi-item and single scales, including five functional scales (physical, role, emotional, social, and cognitive), three symptom scales (fatigue, nausea and vomiting, and pain), a global health status/quality of life (GHS/QoL) scale, and six single items (dyspnea, insomnia, appetite loss, constipation, diarrhea, and financial difficulties). Subjects rate items on a four-point scale, with 1 as "not at all" and 4 as "very much." The EORTC QLQ-C30 was developed and validated for use in a cancer subject population, and its reliability and validity is highly consistent across different language cultural groups. A change of 5 – 10 points is considered a small change, and the lower bound (5) is being used to define the minimum important difference (MID). A change of 10 – 20 points is considered a moderate change.

EORTC QLQ-CLL16

The EORTC QLQ-CLL16 was designed specifically for subjects with stage 0 to stage 4 CLL.³⁷ It is comprised of sixteen questions that address five domains of HRQoL important in CLL. There are three multi-item scales assessing Fatigue (2 items), Disease and Treatment Effects (7 items), and Infection (5 items), and two single-item scales assessing Social Activities and Future Health Worries. Subjects rate items on a four-point scale, with 1 as "not at all" and 4 as "very much." A negative change in score from baseline represents an improvement in symptoms. A change of 5 – 10 points is considered a small change, and the lower bound (5) is being used to define the minimum important difference (MID). A change of 10 – 20 points is considered a moderate change.³⁸⁻⁴⁰

EQ-5D-5L

The EuroQol EQ-5D-5L is a generic preference instrument that has been validated in numerous populations.^{41,42} The EQ-5D-5L has five dimensions: mobility, self-care, usual activities, pain/discomfort and anxiety/depression. These dimensions are measured on a five-level scale: no problems, slight problems, moderate problems, severe problems, and extreme problems. The scores for the 5 dimensions are used to compute a single utility index score ranging from zero (0.0) to 1 (1.0) representing the general health status of the individual. The EQ-5D-5L also contains a visual analog scale (VAS) to assess the subject's overall health. The MID for the EQ-5D utility index score in cancer subjects is 0.08, and the MID for EQ-5D VAS is 7.^{43,44}

Each of the five dimensions of the EQ-5D-5L, the VAS and overall utility score will be calculated using the EuroQol scoring manual, and summarized (mean, std. dev., median) at each assessment. The impact of treatment over time will be assessed by calculating the change in score from baseline at each assessment time point.

5.3.2.2.2 Disease Assessments

For disease assessments, response will be assessed by the investigator based on analysis of clinical laboratory tests (hematology laboratory values), disease assessment physical examination, CT scan including neck, chest, abdomen, and pelvis (or MRI if CT with contrast is medically contraindicated); a bone marrow aspirate and biopsy is not required but results will be recorded if available. Subjects will be evaluated against the 2008 Modified IWCLL NCI-WG Criteria for Tumor Response⁴⁶ with the addition of CT imaging (or MRI). A BM assessment is required to confirm CR.

At screening (baseline), all measurable disease must be documented by laboratory testing (hematologic status), physical examination, and CT scan. All baseline evaluations should be performed as closely as possible to the beginning of treatment and not more than 4 weeks before the beginning of the treatment with the exception of the CT scan (or MRI) which will be accepted if previously performed within 35 days prior to study drug initiation. During the study, subjects will have a disease assessment at Week 24, Week 36

and Week 48. To confirm the response, a CT scan will be performed at Week 48 on all subjects. For subjects with CR as response at Week 48, a BM is required to confirm the response.

Methods of Measurement

Disease response and progression will be assessed by analysis of peripheral blood, clinical examination, radiographic scans and bone marrow aspirate and biopsy.

The same method of assessment and the same technique should be used to characterize each identified and reported lesion at baseline and during follow-up.

A full disease assessment physical examination should be performed to assess the extent of disease involvement. Physical examinations should include the evaluation of the presence and degree of enlarged lymph nodes in two dimension (cervical, supraclavicular, axillary, inguinal and femoral nodes), hepatomegaly, and splenomegaly. These should be noted on all examinations irrespective of being present or absent. All measurements should be taken and recorded in metric notation using a ruler or calipers. Clinical lesions will only be considered measurable when they are superficial (e.g., palpable lymph nodes). The diameter, in two planes, of the largest palpable nodes in each of the following sites should be measured: cervical, supraclavicular, axillary, inguinal, and femoral. The presence of hepatomegaly and splenomegaly should be performed.

The 12 largest bi-dimensional lesions should be recorded in the eCRF.

- Target Lesions: A maximum of 12 target lesions may be selected (up to 6 nodal and 6 extra nodal). Target nodal lesions must be abnormal (> 1.5 cm in LDi [Longest Diameter at baseline]), clearly measurable and suitable for consistent, reproducible measurement in at least two perpendicular dimensions. Target extra nodal lesions must be > 1 cm in two perpendicular diameters at baseline.
- Non-Target Lesions: Sites will be classified as non-target lesions where disease is present but not selected for target lesions. A maximum of 10 non-target lesions can be selected. Non-target nodal lesions must be

abnormal (> 1.5 cm in LD_i at baseline). Non-target extra nodal lesions must be > 1 cm in two perpendicular diameters. Nodal and extra nodal lesions that were not selected as target lesions at baseline can be followed as non-target lesions.

Computed tomography (CT) is the preferred method to measure lesions selected for response assessment. CT scans (with contrast) should include neck, chest, abdomen, and pelvis scans. CT scans for response assessment may be limited to areas of prior involvement only, if required by local regulatory authorities. A contrast-enhanced MRI of the neck, chest, abdomen and pelvis with a non-contrast CT scan of the chest may be used if CT with contrast is medically contraindicated (e.g., severe contrast allergy). If MRIs are used instead of CT scans, MRIs should be used consistently throughout the study. Conventional CT and MRI should be performed with cuts of 5 mm or less in slice thickness contiguously. Spiral CT should be performed by use of 5 mm contiguous reconstruction algorithm; this specification applies to the regions of the neck, chest, abdomen and pelvis at baseline and follow ups. The 12 largest bi-dimensional lesions should be recorded in the eCRF (6 nodal and 6 extra nodal).

For accurate overall response evaluation, ultrasound (US) should not be used to measure tumor lesions.

Details on bone marrow biopsy and aspirate are provided in Section 5.3.1.1. Study Procedures.

Tumor Response Criteria

Complete Remission (CR)

CR requires all of the following criteria:

- Peripheral blood lymphocytes (evaluated by blood and differential count) below $4 \times 10^9/L$ (4000/ μ L)
- Absence of lymphadenopathy (nodes > 15 mm in longest diameter or any extra nodal disease) by physical examination and CT scan

- No hepatomegaly or splenomegaly by physical examination (as determined by measurement below the relevant costal margin)
- Absence of disease or constitutional symptoms (B symptoms: unexplained fevers > 38°C or 100.4°F, drenching night sweats, > 10% body mass weight loss in the preceding 6 months)
- Blood counts above the following laboratory values:
 - Neutrophils > $1.5 \times 10^9/L$ [1500/ μ L] (without the need for exogenous growth factors)
 - Platelets > $100 \times 10^9/L$ [100,000/ μ L] (without the need for platelet transfusion or exogenous growth factors)
 - Hemoglobin > 110 g/L [11 g/dL] (without the need for blood transfusions or exogenous erythropoietin)
- Bone marrow at least normocellular for age, < 30% of nucleated cells being lymphocytes. Lymphoid nodules should be absent. Bone marrow aspirate and biopsy should be performed after CR/CRi has been achieved. If the bone marrow is hypocellular, a repeat determination should be made in 4 weeks or when peripheral blood counts have recovered. A marrow biopsy should be compared to a pre-treatment marrow if available. Subjects who are otherwise in a complete remission, but bone marrow nodules can be identified histologically should be considered to be nodular PR (nPR). Immunohistochemistry (IHC) should be performed to define whether these nodules are composed of primarily T cells or lymphocytes other than CLL cells, or CLL cells.

Complete Remission with Incomplete Marrow Recovery (CRi)

Subjects who fulfill the criteria for CR (including bone marrow) but who have persistent cytopenia (anemia or thrombocytopenia or neutropenia) apparently unrelated to CLL but related to drug toxicity will be considered CRi. The marrow evaluation described above should be performed with scrutiny and not show any clonal infiltrate.

Partial Remission (PR)

To be considered a PR at least 2 of the following must be met:

- $\geq 50\%$ decrease in peripheral blood lymphocyte count from the pretreatment baseline value.
- $\geq 50\%$ reduction in lymphadenopathy.
- $\geq 50\%$ reduction in the enlargement of the liver and/or spleen (if abnormal prior to therapy).

In addition at least **one** of the following criteria must be met:

- Neutrophils $> 1,500/\mu\text{L}$ or $\geq 50\%$ improvement over baseline.
- Platelets $> 100,000/\mu\text{L}$ or $\geq 50\%$ improvement over baseline.
- Hemoglobin $> 11.0 \text{ g/dL}$ or $\geq 50\%$ improvement over baseline without transfusions or exogenous growth factors.

Table 5. 2008 Modified IWCLL NCI-WG Criteria for Tumor Response

Parameter	Complete Remission (CR) All Criteria Must be Met ^a	Partial Remission (PR) at Least 2 Criteria from Group A AND at Least 1 Criterion from Group B Must be Met	Progressive Disease (PD) at Least 1 Criterion from Group A OR 1 Criterion from Group B Must be Met ^b	Stable Disease (SD) All Criteria Must be Met
Group A				
Lymphadenopathy	None > 1.5 cm	Decrease \geq 50% ^c	Increase \geq 50% ^d or any new LN > 1.5 cm	Change of -49% to +49% ^e
Blood Lymphocytes	< 4000/ μ L	Decrease \geq 50% from baseline	Increase \geq 50% over baseline (\geq 5000/ μ L)	Change of -49% to +49%
Hepatomegaly ^f	None	Decrease \geq 50%	Increase \geq 50% ^g	Change of -49% to +49%
Splenomegaly ^f	None	Decrease \geq 50%	Increase \geq 50% ^g	Change of -49% to +49%
Marrow	Normocellular, < 30% lymphocytes, no B lymphoid nodules; hypocellular marrow defines CRi	N/A	N/A	N/A
Group B				
Platelet Count	> 100,000/ μ L ^h	> 100,000/ μ L or increase \geq 50% over baseline ^h	Decrease of \geq 50% from baseline secondary to CLL	Change of -49% to +49%
Hemoglobin	> 11.0 g/dL ^h	> 11.0 g/dL or increase \geq 50% over baseline ^h	Decrease of > 2 g/dL from baseline secondary to CLL	Increase to \leq 11.0 g/dL over baseline, or decrease < 2 g/dL
Neutrophils	> 1500/ μ L ^h	> 1500/ μ L or increase \geq 50% over baseline ^h	Decrease \geq 50% from baseline secondary to CLL	N/A
New Lesions	None	None	Appearance of new palpable lymph nodes (> 1.5 cm in longest diameter) or any new extra nodal lesion (regardless of size) or transformation to a more aggressive histology, e.g., Richter Syndrome ^d	None

Table 5. 2008 Modified IWCLL NCI-WG Criteria for Tumor Response (Continued)

Parameter	Complete Remission (CR) All Criteria Must Be Met ^a	Partial Remission (PR) at Least 2 Criteria from Group A AND at Least 1 Criterion from Group B Must Be Met	Progressive Disease (PD) at Least 1 Criterion from Group A OR 1 Criterion from Group B Must Be Met ^b	Stable Disease (SD) All Criteria Must Be Met
Other Considerations				
Non-Target Lesions	Nodes must be normal size as visually estimated; extra nodal and other assessable disease should be absent	No change/decreased	Unequivocal progression	No change or decrease or non-substantial increase
Target Extra Nodal Disease	Absence of any extra nodal disease by physical examination (palpable, visualized extra nodal) and CT scan	≥ 50% decrease in SPD	≥ 50% increase in the longest diameter of any extra nodal lesion	Not CR, CRi, PR, or PD

CLL = chronic lymphocytic leukemia; LN = lymph nodes; N/A = Not applicable; SPD = sum of the products of diameters; CRi = complete remission with incomplete marrow recovery

- a. CR also requires the lack of disease-related constitutional symptoms.
- b. Transformation to a more aggressive histology (e.g., Richter Syndrome) would also qualify as a PD.
- c. Sum of the products of multiple LNs (as evaluated by CT scans). Note in eCRF if by physical examination only.
- d. Increase in SPD of multiple nodes, or in greatest diameter of any previous site, or appearance of any new lymphadenopathy or organomegaly. Degree of change in LN or lymphocyte counts should be measured from nadir (lowest post-treatment) values.
- e. Sum products of up to 6 LNs or LN masses (target lesions), with no increase in an LN or new enlarged LN. Increase of < 25% in small LNs (< 2 cm) not significant. Decreases should be measured compared to baseline (pre-treatment) values.
- f. If enlarged before therapy.
- g. An increase in the previously noted enlargement of the liver or spleen by 50% or more or the de novo appearance of hepatomegaly or splenomegaly.
- h. Without the need for exogenous growth factors or transfusions.

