For all subjects, clinical response will be assessed by the Investigator at Week 24, Week 36 and Week 48. Disease response will be based on the analysis of clinical laboratory tests and a disease assessment physical examination. To confirm the response, a contrast-enhanced CT scan (or MRI, if CT scan with contrast is medically contraindicated) will be performed at Week 48 for all subjects. Subjects will be evaluated using the 2008 Modified IWCLL NCI-WG criteria for Tumor Response with the addition of CT imaging (or MRI).

For determination of CR, the CT scan and bone marrow are required to be negative, per the IWCLL NCI-WG criteria. It is recommended that the CT scan is performed first; if it does confirm a clinical response, then a bone marrow biopsy will be obtained. If a CT scan is performed and does not confirm a clinical response, a bone marrow biopsy should not be obtained.

If a subject exhibits clinical signs of possible disease progression (i.e., increased or *de novo* enlargement of liver, spleen or lymph nodes on physical examination) without an increase in lymphocytes meeting the progression of disease criteria, then additional assessments including contrast-enhanced CT scan and/or bone marrow can be performed to confirm or rule out disease progression

The same method of assessment and the same technique should be used to characterize each identified and reported lesion at baseline and during follow-up.

For any subject who has not experienced progressive disease (PD) at the time of permanent discontinuation of venetoclax, follow up phone calls will continue until death, discontinuation from the study or upon study completion.

Response criteria definitions are outlined in 2008 Modified IWCLL-WG Criteria for Tumor Response. See [Table 5](#).

NOTE: Disease assessments may be performed approximately 7 days prior to the scheduled visit.

For patients with Partial Remission at Week 48 an additional CT scan and a bone marrow examination can be done between Week 48 and Week 108 to confirm CR if there is a possibility that a patient achieved Complete Remission based on laboratory tests and a disease assessment physical examination.

Computed Tomography Scans (or Magnetic Resonance Imaging)

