5.3.2.3 Definition of Disease Progression

Disease progression according to 2008 Modified IWCLL NCI-WG Criteria for Tumor Response is characterized by at least one of the following:

- Appearance of any new lesion, such as enlarged lymph nodes (> 1.5 cm), splenomegaly, hepatomegaly, or other organ infiltrates. An increase by 50% or more in greatest determined diameter of any previous site.
- An increase in the previously noted enlargement of the liver or spleen by 50% or more or the de novo appearance of hepatomegaly or splenomegaly.
- An increase in the number of blood lymphocytes by 50% or more with at least 5,000 B lymphocytes per microliter. The increase should be assessed against the best response while on study.
- Transformation to a more aggressive histology (e.g., Richter's Syndrome). Whenever possible, this diagnosis should be confirmed by lymph node biopsy. For subjects experiencing disease progression due to Richter's Syndrome while on study, supplemental data may be collected.
- Occurrence of cytopenia (neutropenia, anemia or thrombocytopenia) attributable to CLL.

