10.1.2 Definitions for Efficacy Endpoints

Complete Remission Rate (CR + CRi)

Complete response rate, complete remission (CR) or complete remission with incomplete marrow recovery (CRi), will be defined as the proportion of subjects who achieved per the 2008 Modified IWCLL NCI-WG criteria as assessed by investigator using the best response at any time during the study. In addition, the 95% confidence interval for complete response rate (CR) rate based on the binomial distribution (Clopper-Pearson exact method) will be provided. Subjects who do not achieve a CR or CRi will be considered to be non-responders in the calculation of complete response rate.

Overall Response Rate (ORR)

ORR (CR + CRi + nPR + PR) will be defined as the proportion of subjects who achieved complete remission (CR), complete remission with incomplete marrow recovery (CRi), nodular partial remission (nPR), or confirmed partial remission (PR) based on the 2008 Modified IWCLL NCI-WG criteria as assessed by investigator using the best response at any time during the study. The corresponding exact 95% confidence interval for the proportion (Clopper-Pearson exact method) will be constructed. Subjects who do not respond will be considered non-responders.

Duration or Response (DOR)

The DOR for a given subject will be defined as the number of days from the day the criteria are met for CR, CRi, nPR, or PR (whichever is recorded first) to the earliest date that progressive disease (PD) is objectively documented (radiographic or clinical) or death

(i.e., DoR = PD/death/censoring date – earliest CR/CRi/nPR/PR date + 1 day). For subjects who have a PR before CR, CRi, or nPR in subsequent visits, the DOR is computed from the earliest PR. If a subject is still responding then the subject's data will be censored at the date of the last available disease evaluation or at the cut-off date for the interim analysis if the subject has a disease evaluation that is after the cut-off date. Only subjects with the iWCLL response criteria will be included in the analysis of DOR. The distribution of the duration of overall response will be estimated using the Kaplan-Meier methodology. Median duration of response will be calculated and the corresponding 95% confidence interval will be presented.

Time to Progression (TTP)

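### Table 5 lets the absence of new lesions stand in for the blood-count requirement for PR, which the PR text of Section 5.3.2.2.2 does not allow

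*Protocol*

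**What the plan says.** **Table 5 (Protocol 5.3.2.2.2).** The PR column header asks for "at Least 2 Criteria from Group A AND at Least 1 Criterion from Group B Must be Met". Four rows stand under the Group B label: Platelet Count, Hemoglobin, Neutrophils and New Lesions. The next label, Other Considerations, comes only after them. The PR cell for New Lesions reads *None*. The PD header asks for "at Least 1 Criterion from Group A OR 1 Criterion from Group B Must be Met", and the PD cell for New Lesions begins "Appearance of new palpable lymph nodes (> 1.5 cm in longest diameter) or any new extra nodal lesion (regardless of size".

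**PR text (same section, above the table).** There are two steps. The first is "To be considered a PR at least 2 of the following must be met", listing lymphocyte count, lymphadenopathy, and liver or spleen. The second is "In addition at least one of the following criteria must be met", listing neutrophils, platelets and hemoglobin. New lesions are not mentioned in either list.

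**Progression (5.3.2.3).** One listed feature is enough, and the first is "Appearance of any new lesion, such as enlarged lymph nodes (> 1.5 cm), splenomegaly, hepatomegaly, or other organ infiltrates".

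**Which definition the sites use.** Protocol 5.3.1.1 says "Response criteria definitions are outlined in 2008 Modified IWCLL-WG Criteria for Tumor Response" and then points to Table 5.

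**Where PR enters the analysis.** SAP 10.1.2 states "ORR (CR + CRi + nPR + PR) will be defined as the proportion of subjects who achieved complete remission (CR", continuing through CRi, nPR and PR, as assessed by the investigator and taken as best response. The same section starts DOR at the first CR, CRi, nPR or PR.

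**The concern.** The protocol gives two definitions of PR in one section, and they sort the same subject differently. The text has a nodal, organ or lymphocyte part and a hematologic part, and both are required. In the table, New Lesions counts as a Group B item for which *None* is the qualifying entry. Almost any subject without a new lesion then satisfies the second part automatically, and the hematologic requirement drops out.

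Response is judged by investigators at about 43 sites, who are referred to the table. The SAP describes no derivation from recorded counts and lesions that would correct a PR based on the table alone. ORR, a key secondary endpoint in Protocol 8.1.2.2, would then depend on which definition a site followed. DOR would gain subjects, or start earlier, for cases that are not PR under the text.

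**Working it through.** The documents state no figure that rests on this rule, so there is none to reproduce. The check is one of classification.

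**Inputs.** At least two Group A PR criteria are taken as met. Let P, H and N be 1 if the platelet, hemoglobin or neutrophil criterion is met and 0 if not. Let L be 1 if there is a new lesion and 0 if not. This gives 2 × 2 × 2 × 2 = 16 combinations.

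**Rules.**
- Table 5 read literally: PR if P + H + N + (1 − L) ≥ 1.
- PR text: PR if P + H + N ≥ 1.
- PD on the new lesion alone (Table 5 PD column, Section 5.3.2.3): L = 1.
- Proposed rule: PR if P + H + N ≥ 1 and L = 0.

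**Results.**

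| Rule | Meets PR wording (of 16) | Also PD | PR if PD overrides |
|---|---|---|---|
| Table 5, literal | 15 | 7 | 8 |
| PR text | 14 | 7 | 7 |
| Proposed | 7 | 0 | 7 |

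The table fails only P = H = N = 0 with L = 1, so 16 − 1 = 15. The text fails P = H = N = 0 for either value of L, so 16 − 2 = 14. The one disagreement is P = H = N = 0 with L = 0: PR by the table, not PR by the text.

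Eight combinations have a new lesion. Seven of them meet the PR wording, under the table and the text alike, and all eight are PD. The Group B placement therefore does not create the overlap between PR and PD.

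**Can the disagreement case occur?** Protocol 5.2.1 admits platelets from 25,000/mm³ and hemoglobin from 8.0 g/dL, and its marrow criterion sets no neutrophil minimum. Section 6.1.9.3 says venetoclax may cause neutropenia. Footnote h of Table 5 does not accept counts that need growth factors or transfusions, both of which Section 5.2.3 permits. The 50% improvement route narrows the group. From 25,000/mm³, unsupported platelets need only reach 25,000 × 1.5 = 37,500/mm³. For hemoglobin at the entry floor it adds nothing, since 8.0 × 1.5 = 12.0 g/dL already exceeds the absolute threshold of 11.0.

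**Scale.** With 200 subjects, k affected subjects raise ORR by k/200, or 0.5 percentage points each. The documents do not give k. As a yardstick only, take an ORR of 75%, the dose-escalation figure in Protocol Section 3.0. The exact 95% interval for 150/200 is 68.4% to 80.8%, a half-width of (80.8 − 68.4)/2 = 6.2 points. It would take about 6.2/0.5 ≈ 12 such subjects to move ORR by that much.

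**The case against.** **The text is explicit and stands just above the table.** A careful investigator would read the two together and require a blood count. That is fair, and it makes this a contradiction between table and text, not an unopposed rule. It does not remove the problem, because Section 5.3.1.1 names the table as the place where the definitions are found. A ruled line or shading might set the New Lesions row apart on the page, but no group label does. The amendment log records a deleted heading in this table without showing where it stood, so nothing here rests on the log.

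**The affected group is narrow.** A subject must have two Group A responses and fail all three counts, on both the absolute and the relative test. This stands, and it is why no size is claimed.

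**The stakes are modest.** The Synopsis calls the analyses descriptive, ORR receives only an exact confidence interval, and the primary endpoint is quality of life. This also stands.

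**A stronger reading: progressors count as responders.** A reader might infer this because only one Group B item is needed, which leaves *None* optional for PR. The documents do not support it. A new lesion is PD on its own under the Table 5 PD column and Section 5.3.2.3, and a new enlarged node is also PD under the Lymphadenopathy row and footnote d. What is missing is only a sentence that PD prevails when both wordings are met.

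**A second stronger reading: PD never reaches extra nodal or non-target disease**, because those rows lie outside Groups A and B. This goes too far. Section 5.3.2.3 defines progression without the groups and covers a 50% increase in diameter at any previous site. The non-target entry is itself printed in the PD column.

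**Conclusion.** Wrong as written. Table 5 and the PR text give different definitions of PR, and with two Group A criteria met they part in exactly one case: no blood-count criterion met and no new lesion. The direction is certain. Wherever the table is followed in place of the text, PR and ORR can only go up, and DOR can begin at an assessment that is not a response under the text. The amount is not known. It depends on how many subjects fall in that case and how many sites apply the table literally, and the documents give neither. Each subject is worth 0.5 points of ORR if 200 are analysed.

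TTP, PFS and OS do not use PR and are unaffected, as is the primary endpoint. On new lesions the gap is smaller: the plan already classes them as PD but does not say that PD overrides PR. The conclusion assumes that the group labels in Table 5 mean what the column headers say they mean.

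**What to change.** 1. In Table 5, take New Lesions out of the Group B count, so that Group B for PR is platelets, hemoglobin and neutrophils, as in the PR text.
2. Make absence of new lesions a separate, mandatory condition for PR, in both the table and the text.
3. State once that any PD criterion, in Table 5 or Section 5.3.2.3, overrides PR.
4. Before the ORR analysis, check each investigator-assessed PR against the recorded counts and lesions, and query discrepancies with the site. The endpoint remains the investigator's assessment, so the SAP should say how an unresolved query is handled.

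The cost is a few lines of wording and one programmed listing on data already collected. ORR may come out slightly lower, and some DOR start dates may move or drop out.
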